4.5.1.7 Management Algorithms for Immuno-oncology Agents

Immuno-oncology (I-O) agents are associated with AEs that can differ in severity and duration than AEs caused by other therapeutic classes. Nivolumab and ipilimumab are considered I-O agents in this protocol. Early recognition and management of AEs associated with I-O agents may mitigate severe toxicity. Management algorithms have been developed to assist investigators in assessing and managing the following groups of AEs:

- Gastrointestinal
- Renal
- Pulmonary
- Hepatic
- Endocrinopathy
- Skin
- Neurological
- Myocarditis

The above algorithms are found in the nivolumab IB and Appendix 1 of this protocol.

4.5.1.8 Treatment of Nivolumab- or Ipilimumab-Related Infusion Reactions

Since nivolumab and ipilimumab contain only human immunoglobulin protein sequences, they are unlikely to be immunogenic and induce infusion or hypersensitivity reactions. However, if such a reaction were to occur, it might manifest with fever, chills, rigors, headache, rash, pruritus, arthralgias, hypotension, hypertension, bronchospasm, or other allergic-like reactions. All Grade 3 or 4 infusion reactions should be reported within 24 hours to the study medical monitor and reported as an SAE if it meets the criteria. Infusion reactions should be graded according to NCI CTCAE version 4 guidelines.

Treatment recommendations are provided below and may be modified based on local treatment standards and guidelines, as appropriate:

For Grade 1 symptoms: (mild reaction; infusion interruption not indicated; intervention not indicated):

• Remain at bedside and monitor subject until recovery from symptoms. The following prophylactic premedications are recommended for future infusions: diphenhydramine 50 mg (or equivalent) and/or acetaminophen/paracetamol 325 to 1000 mg at least 30 minutes before additional nivolumab or ipilimumab administrations.

For Grade 2 symptoms: (moderate reaction required therapy or infusion interruption but responds promptly to symptomatic treatment (eg, antihistamines, non-steroidal anti-inflammatory drugs, narcotics, corticosteroids, bronchodilators, IV fluids); prophylactic medications indicated for ≤ 24 hours):

- Stop the nivolumab or ipilimumab infusion, begin an IV infusion of normal saline, and treat the subject with diphenhydramine 50 mg IV (or equivalent) and/or acetaminophen/paracetamol 325 to 1000 mg; remain at bedside and monitor subject until resolution of symptoms. Corticosteroid and/or bronchodilator therapy may also be administered as appropriate. If the infusion is interrupted, then restart the infusion at 50% of the original infusion rate when symptoms resolve; if no further complications ensue after 30 minutes, the rate may be increased to 100% of the original infusion rate. Monitor subject closely. If symptoms recur, then no further nivolumab or ipilimumab will be administered at that visit.
- For future infusions, the following prophylactic premedications are recommended: diphenhydramine 50 mg (or equivalent) and/or acetaminophen/paracetamol 325 to 1000 mg should be administered at least 30 minutes before nivolumab or ipilimumab infusions. If necessary, corticosteroids (up to 25 mg of hydrocortisone or equivalent) may be used.

For Grades 3 or 4 symptoms: (severe reaction, Grade 3: prolonged [ie, not rapidly responsive to symptomatic medication and/or brief interruption of infusion]; recurrence of symptoms following initial improvement; hospitalization indicated for other clinical sequelae (eg, renal impairment, pulmonary infiltrates). Grade 4: Life-threatening; pressor or ventilatory support indicated):

• Immediately discontinue infusion of nivolumab or ipilimumab. Begin an IV infusion of normal saline and treat the subject as follows: Recommend bronchodilators, epinephrine 0.2 to 1 mg of a 1:1000 solution for subcutaneous administration or 0.1 to 0.25 mg of a 1:10,000 solution

injected slowly for IV administration, and/or diphenhydramine 50 mg IV with methylprednisolone 100 mg IV (or equivalent), as needed. Subject should be monitored until the Investigator is comfortable that the symptoms will not recur. Nivolumab or ipilimumab will be permanently discontinued. Investigators should follow their institutional guidelines for the treatment of anaphylaxis. Remain at bedside and monitor subject until recovery of the symptoms.

In case of late-occurring hypersensitivity symptoms (eg, appearance of a localized or generalized pruritus within 1 week after treatment), symptomatic treatment may be given (eg, oral antihistamine or corticosteroids.

4.5.2 Nivolumab plus Chemotherapy Arm

4.5.2.1 Nivolumab plus Chemotherapy Arm Dosing Schedule

Subjects randomized to the nivolumab-plus-chemotherapy arm should receive either nivolumab 360 mg plus XELOX or nivolumab 240 mg plus FOLFOX.

- Subjects assigned to nivolumab plus-XELOX will receive nivolumab 360 mg administered IV over 30 minutes and oxaliplatin 130 mg/m² administered IV on Day 1 of each treatment cycle every 3 weeks, and capecitabine 1000 mg/m² administered orally twice daily (ie, 1000 mg/m² in the morning and 1000 mg/m² in the evening) on Days 1 to 14 of each treatment cycle every 3 weeks (see Table 4.5.2.1-1). Dosing windows for subsequent XELOX doses should adhere to recommendations in the prescribing information or local standards, where indicated.
- Premedication is not usually required in the first cycle. For subsequent cycles, adequate premedication may be administrated per local standard.
- Capecitabine should be taken with food.

Table 4.5.2.1-1: Dose Schedule of Nivolumab-plus-XELOX						
Treatment group	Drug name	Cycle 1 (Week 1)	Cycle 2 (Week 4)	Cycle 3 (Week 7)	Cycle 4 (Week 10)	Cycle 5 (Week 13) till EOT (Q3 weeks)
Nivolumab- plus-XELOX	Nivolumab 360 mg	Day 1	Day 1	Day 1	Day 1	Day 1
	Oxaliplatin 130 mg/m ²	Day 1	Day 1	Day 1	Day 1	Day 1
	Capecitabine 1000 mg/m ² twice daily	Days 1 to 14	Days 1 to 14			

• Subjects assigned to nivolumab-plus-FOLFOX will receive nivolumab 240 mg administered IV over 30 minutes and oxaliplatin 85 mg/m², leucovorin 400 mg/m², and fluorouracil 400 mg/m² administered IV on Day 1 of each treatment cycle every 2 weeks, and fluorouracil

1200 mg/m² IV continuous infusion over 24 hours daily or per local standard on Days 1 and 2 of each treatment cycle every 2 weeks (see Table 4.5.2.1-2). Dosing windows for subsequent FOLFOX doses should adhere to recommendations in the prescribing information or local standards, where indicated.

Premedication is not usually required in the first cycle. For subsequent cycles, adequate premedication may be administrated per local standard.

Table 4.5.2.1	Table 4.5.2.1-2: Dose Schedule of Nivolumab-plus-FOLFOX						
Treatment group	Drug name	Cycle 1 (Week 1)	Cycle 2 (Week 3)	Cycle 3 (Week 5)	Cycle 4 (Week 7)	Cycle 5 (Week 9) till EOT (Q2 weeks)	
	Nivolumab 240 mg	Day 1					
	Oxaliplatin 85 mg/m ²	Day 1					
Nivolumab- plus-FOLFOX	Leucovorin 400 mg/m ²	Day 1					
	Fluorouracil 400 mg/m ²	Day 1					
	Fluorouracil 1200 mg/m ²	Days 1 & 2					

• No cross-over will be allowed between XELOX and FOLFOX in this study.

When study drugs (nivolumab and chemotherapy) are to be administered on the same day, nivolumab is to be administered first. Nivolumab infusion must be promptly followed by a flush of diluent to clear the line of nivolumab before starting the chemotherapy infusion(s). The second infusion will always be the chemotherapy study drug(s) and will start after the infusion line has been flushed, filters changed and the patient has been observed to ensure no infusion reaction has occurred. The time between infusions is expected to be approximately 30 minutes but may be more or less depending on the situation.

The treatment with nivolumab will be given for up to 24 months in the absence of disease progression or unacceptable toxicity. Chemotherapy will be given as per the study dosing schedule.

4.5.2.2 Dose Modification Criteria for Nivolumab-plus-Chemotherapy

Dose modification criteria for the combination regimen should follow the respective individual dose modification criteria of each component. For chemotherapy, it is allowed to follow local standard or local package insert recommendations.

Dosing for all drugs should be delayed/interrupted if any criteria in Sections 4.5.1.2 (for nivolumab) or Sections 4.6.2.2 (for XELOX) and 4.6.2.3 (for FOLFOX.) are met.

Dose reduction of nivolumab are not permitted. Dose reduction for chemotherapy is permitted according to local standard or local package insert. See also Sections 4.6.2.2 for XELOX and 4.6.2.3 for FOLFOX.

Subjects may resume dosing when resuming criteria for BOTH nivolumab (Section 4.5.1.4) and chemotherapy (Section 4.6.2.2 for XELOX and Section 4.6.2.3 for FOLFOX) are met. That is, nivolumab and chemotherapy must be administered together until treatment discontinuation. It is allowed to administer either nivolumab or chemotherapy doublet or single drug alone if the other(s) are delayed or discontinued due to toxicity which is not overlapping for nivolumab and chemotherapy, judging by the treating investigator if it is the best interest in the subjects.

The assessments for discontinuation of nivolumab and/or chemotherapy should be made separately. Nivolumab discontinuation criteria are detailed in Section 4.5.1.5, and chemotherapy discontinuation criteria are detailed in Sections 4.6.2.2 (for XELOX) and 4.6.2.3 (for FOLFOX). Continuation of nivolumab alone when chemotherapy has been discontinued due to toxicity is permitted. Chemotherapy doublet or single drug is allowed to continue if the discontinuation criteria for nivolumab is met.

From Amendment 29, nivolumab 480 mg Q4W is permitted when all chemotherapy components are discontinued and nivolumab is continued alone. Subjects must be in the study for a minimum of 6 months from Cycle 1, Day 1 before switching to 480 mg Q4W nivolumab. Nivolumab 480 mg should be given 2 weeks or 3 weeks following the last administration of nivolumab 240 mg Q2W or 360 mg Q3W, respectively.

Subjects treated with nivolumab-plus-chemotherapy will be permitted to continue nivolumab treatment beyond initial RECIST 1.1-defined PD, assessed by the investigator, as long as they meet the criteria described in Section 4.5.1.6. The management of nivolumab-related adverse events and infusion reactions should follow instructions listed in Section 4.5.1.7 and 4.5.1.8.

4.6 Chemotherapy Arm Dosing

4.6.1 Oxaliplatin-Plus-Fluoropyrimidine Dose and Schedule

Subjects randomized to the chemotherapy arm should receive either XELOX or FOLFOX:

• Subjects assigned to XELOX will receive oxaliplatin 130 mg/m² administered IV on Day 1 of each treatment cycle and capecitabine 1000 mg/m² administered orally twice daily (ie, 1000 mg/m² in the morning and 1000 mg/m² in the evening) on Days 1 to 14 of each treatment cycle, every 3 weeks (see Table 4.6.1-1). Dosing windows for subsequent XELOX doses should adhere to recommendations in the current prescribing information or local standards, where indicated.

Premedication is not usually required in the first cycle. For subsequent cycles, adequate premedication may be administrated per local standard.

Capecitabine should be taken with food.

Table 4.6.1-1	Table 4.6.1-1: Dose Schedule of XELOX						
Treatment group	Drug name	Cycle 1 (Week 1)	Cycle 2 (Week 4)	Cycle 3 (Week 7)	Cycle 4 (Week 10)	Cycle 5 (Week 13) till EOT (Q3 weeks)	
XELOX	Capecitabine 1000 mg/m ² twice daily	Days 1 to 14	Days 1 to 14				
	Oxaliplatin 130 mg/m ²	Day 1	Day 1	Day 1	Day 1	Day 1	

• Subjects assigned to FOLFOX will receive oxaliplatin 85 mg/m², leucovorin 400 mg/m², and fluorouracil 400 mg/m² administered IV on Day 1 of each treatment cycle, and fluorouracil 1200 mg/m² IV continuous infusion over 24 hours daily or per local standard on Days 1 and 2 of each treatment cycle, every 2 weeks (see Table 4.6.1-2). Dosing windows for subsequent FOLFOX doses should adhere to recommendations in the prescribing information or local standards, where indicated.

Premedication is not usually required in the first cycle. For subsequent cycles, adequate premedication may be administrated per local standard.

Table 4.6.1-2	Table 4.6.1-2: Dose Schedule of FOLFOX					
Treatment group	Drug name	Cycle 1 (Week 1)	Cycle 2 (Week 3)	Cycle 3 (Week 5)	Cycle 4 (Week 7)	Cycle 5 (Week 9) till EOT (Q2 weeks)
FOLFOX	Oxaliplatin 85 mg/m ²	Day 1				
	Leucovorin 400 mg/m ²	Day 1				
	Fluorouracil 400 mg/m ²	Day 1				
	Fluorouracil 1200 mg/m ²	Days 1 & 2				

• No cross-over will be allowed between XELOX and FOLFOX in this study.

4.6.2 Dose Modification Criteria for Oxaliplatin-Plus-Fluoropyrimidine Treatment

Dose modifications of oxaliplatin, capecitabine, leucovorin, and fluorouracil are permitted according to local standards or local package inserts.

Clinical Protocol BMS-936558

4.6.2.1 General Guidance for Dose Modification for Chemotherapy

- Treatment for the first cycle should only commence if all the inclusion criteria are met and the subject has been enrolled. For subsequent cycles, dose delay/modification is permitted per local standard or as described in Section 4.6.2.2 and Section 4.6.2.3.
- Doses of any study drug omitted for toxicity are not replaced or restored; instead, the patient should resume the planned treatment cycles. Supportive care (for example, colony-stimulating factors [CSFs], blood and blood products, etc. can be administered in accordance with the latest American Society of Clinical Oncology (ASCO) or other equivalent guidelines.
- Dose modification, for non-serious and non-life-threatening toxicities like alopecia, altered taste or nail changes may not be required and the final decision is left to the discretion of the treating investigator.
- In situations where concomitant toxicities of varying severity exist, dose modification will be tailored for the toxicity with highest CTCAE grading.
- If there is a delay or modification in administration of study drug(s) due to toxicity, treatment with the other study agent(s) should continue as scheduled. If clinically appropriate, the investigator can delay all treatment components up to a maximum of 7 days to allow synchronized administration of all agents.

If toxicity related to any component of chemotherapy does not resolve in the same treatment cycle, the administration of that component can be delayed up to 6 weeks. If the toxicity does not resolve within 6 weeks, that component will be discontinued unless it is determined by the treating investigator that the patient might benefit from continuation of the component.

4.6.2.2 Dose Modification Criteria for XELOX

Capecitabine

Toxicity due to capecitabine administration may be managed by symptomatic treatment and/or treatment interruption or dose reduction. Dose modifications of capecitabine are presented in Table 4.6.2.2-1. Once the dose has been reduced, it should not be increased at a later time. For those toxicities considered by the treating physician to be unlikely to become serious or life-threatening, eg alopecia, altered taste, or nail changes, treatment can be continued at the same dose without reduction or interruption. Subjects taking capecitabine should be informed of the need to interrupt treatment immediately if moderate or severe toxicity occurs. Doses of capecitabine omitted for toxicity are not replaced.

Approved v1000

Table 4.6.2.2-1: Recommended Dose Modifications of Capecitabine

Toxicity ^a	During a course of therapy	Dose adjuvant for next treatments (% of starting dose)
Grade 1	Maintain dose level	Maintain dose level
Grade 2		
1st appearance	Interrupt until resolved to	100% (1000 mg/m ²)
2nd appearance	Grade 0 1	75% (750 mg/m ²)
3rd appearance		50% (500 mg/m ²)
4th appearance	Discontinue treatment permanently	-
Grade 3		
1st appearance	Interrupt until resolved to	75% (750 mg/m ²)
2nd appearance	Grade 0 1	50% (500 mg/m ²)
3rd appearance	Discontinue treatment permanently	-
Grade 4		
1st appearance	Discontinue treatment permanently or,	50% (500 mg/m²)
	if physician deems it to be in the patient's best interest to continue, interrupt until resolved to Grade 0 - 1	

According to the National Cancer Institute of Canada Clinical Trial Group (NCIC CTG) Common Toxicity Criteria (version 1) or the Common Terminology Criteria for Adverse Events (CTCAE) of the Cancer Therapy Evaluation Program, US National Cancer Institute, version 4.0.

Oxaliplatin

Dose Modifications for Neurotoxicity

- For Grade 2 peripheral sensory neuropathy (moderate paresthesia or dysesthesia), or limiting instrumental activities of daily living, skip oxaliplatin. When toxicity resolves to ≤ Grade 1, resume oxaliplatin to 75% of initial dose. If oxaliplatin is skipped for 4 weeks (2 consecutive doses) for neurologic toxicity, discontinue oxaliplatin.
- For Grade 3 or greater peripheral sensory neuropathy (severe paresthesia or dysesthesia), or limiting self-care activities of daily living), discontinue oxaliplatin.

Dose Modifications for Subjects with Renal Impairment

- For normal renal function or mild to moderate renal impairment (CrCl > 50 mL/min), the full dose of oxaliplatin can be administered.
- For severe renal impairment, the oxaliplatin dose should be reduced to 75% of initial dose.

Dose Modifications for Subjects with Hematological Toxicity

• For Grade 2 or Grade 3 thrombocytopenia, oxaliplatin should be reduced to 75% of initial dose. For Grade 4 thrombocytopenia, the dose should be reduced to 50% of initial dose.

• For Grade 3 or Grade 4 neutropenia or febrile neutropenia, the oxaliplatin dose should be reduced to 75% of initial dose.

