4.6.2.3 Dose Modification Criteria for FOLFOX

Recommended dose modifications of FOLFOX are provided in Table 4.6.2.3-1 and Table 4.6.2.3-2.

Table 4.6.2.3-1: Recommended Dose Modifications of FOLFOX

Dame	Charting Dage	Dose Modification		
Drug	Starting Dose	Dose Level - 1	Dose Level - 2	
Oxaliplatin	85 mg/m ²	70 mg/m ²	50 mg/m ²	
	Bolus 5-FU: 400 mg/m ²	Bolus 5-FU: 300 mg/m ²	Bolus 5-FU: 200 mg/m ²	
5-FU	Leucovorin: 400 mg/m ²	Leucovorin: 300 mg/m ²	Leucovorin: 200 mg/m ²	
	Infusion 5-FU: 2400 mg/m ² /48 hours	Infusion 5-FU: 2000 mg/m ² /48 hours	Infusion 5-FU: 1600 mg/m ² /48 hours	

5-FU: 5-fluorouracil

Table 4.6.2.3-2: Dose Modifications of FOLFOX

Toxicity	Definition	During a course of therapy	Dose adjustment for next treatments
			Dose level -1
Neutropenia	Grade 3 or greater	Interrupt until resolved to Grade 2	*If treatment delayed for 4 consecutive weeks, discontinue all treatment
			Dose level -1
	Grade 2	Interrupt until resolved to Grade 1	*If Grade 2 persists > 7 days, oxaliplatin reduced by 2 dose levels when platelets improve to Grade 1
			Dose level -1
Thrombocytopenia	Grade 3	Interrupt until resolved to Grade 1	*If Grade 3 persists > 7 days, oxaliplatin reduced by 2 dose levels when platelets improve to Grade 1
			Dose level -2
	Grade 4	Interrupt until resolved to Grade 1	*If Grade 4 persists > 7 days, oxaliplatin reduced by 2 dose levels when platelets improve to Grade 1
			Oxaliplatin dose -1
			Continue 5-FU and leucovorin
Neurologic toxicity	Grade 2 peripheral sensory neuropathy	Interrupt until resolved to Grade 1	*If oxaliplatin delayed for neurologic toxicity for 4 consecutive weeks, discontinue oxaliplatin, continue 5-FU and leucovorin
	Grade 3 or greater peripheral sensory neuropathy	Discontinue oxaliplatin	Continue 5-FU and leucovorin
			Dose level -1
Gastrointestinal toxicities	Grade 2 or greater diarrhea	Interrupt until resolved to Grade 1	If dose delayed for diarrhea for 4 consecutive weeks, discontinue all treatment

For toxicities not listed above, dose modifications are permitted per local standards.

Subjects may also discontinue oxaliplatin following multiple cycles if, in the investigator's judgment, cumulative toxicity is likely to increase over time and become problematic.

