4.7 Criteria for Oxaliplatin-plus-Fluoropyrimidine Discontinuation

Except where specified below, both chemotherapy drugs in the platinum doublet chemotherapy regimen should be discontinued for any of the following:

- Any Grade \geq 4 peripheral neuropathy requires discontinuation of oxaliplatin.
- In case of persistent Grade 3 paraesthesia, oxaliplatin should be discontinued.

• Any Grade ≥ 3 mucocutaneous reaction possibly attributable to capecitabine or leucovorin requires permanent discontinuation.

- Grade \geq 3 drug-related thrombocytopenia associated with clinically significant bleeding
- Any drug-related liver function test (LFT) abnormality that meets the following criteria requires discontinuation:
 - AST or ALT > 5-10 x upper limit of normal (ULN) for > 2 weeks
 - AST or ALT $> 10 \times ULN$
 - Total bilirubin > 5 x ULN
 - Concurrent AST or ALT > 3 x ULN and total bilirubin > 2 x ULN
- Any oxaliplatin-related decrease in creatinine clearance to < 30 mL/min (using the Cockroft Gault formula) requires discontinuation of oxaliplatin.
- Any drug-related AE which recurs after 2 prior dose reductions for the same drug-related AE requires discontinuation of the drug(s) which was/were previously dose reduced.
- Any Grade ≥ 3 drug-related hypersensitivity reaction or infusion reaction requires discontinuation of the drug(s) felt to be causing the reaction. The drug not felt to be related to the hypersensitivity reaction or infusion reaction may be continued.
- Any Grade 4 drug-related AE which the investigator deems is inappropriate to be managed by dose reduction(s) requires discontinuation of the drug(s) felt to be causing the event. The drug not felt to be related to the event may be continued.
- If any toxicity does not resolve within 42 days, that component will be discontinued unless it is determined by the treating investigator that the subject might benefit from continuation of the component.

For toxicities that are not listed above, the treating investigators can decide to discontinue any individual chemotherapy agent or all chemotherapy agents if it is not the best interest in the subject per the local standards.

Post-treatment study follow-up is critically important and is essential to preserving subject safety and the integrity of the study. Subjects who discontinue study treatment will continue to be followed for collection of tumor surveillance assessments, safety, QoL questionnaires and biomarker sampling as per protocol.

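### For a XELOX subject whose creatinine clearance falls below 30 mL/min because of oxaliplatin, Protocol 4.6.2.2 says reduce and 4.7 says discontinue, and the cross-references do not settle which governs

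*Protocol*

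**What the plan says.** Two places in the Protocol give a renal rule for oxaliplatin.

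- Section 4.6.2.2, the XELOX dose-modification section, has two renal bullets. The first reads "For normal renal function or mild to moderate renal impairment (CrCl > 50 mL/min), the full dose of oxaliplatin can be administered". The second reads "For severe renal impairment, the oxaliplatin dose should be reduced to 75% of initial dose". Neither names a cause, and the second carries no clearance value.
- Section 4.7, the discontinuation criteria for oxaliplatin plus fluoropyrimidine, reads "Any oxaliplatin-related decrease in creatinine clearance to < 30 mL/min (using the Cockroft Gault formula) requires discontinuation of oxaliplatin". It does not use the term severe renal impairment.

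Four other places bear on how the two rules fit together.

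- Section 3.5 lists toxicity under 4.5.1.5 and 4.7 among the reasons for which investigational product must be stopped. Section 4.1 classes oxaliplatin as investigational product.
- Section 4.5.2.2, for the nivolumab-plus-chemotherapy arm, says that "chemotherapy discontinuation criteria are detailed in Sections 4.6.2.2 (for XELOX) and 4.6.2.3 (for FOLFOX" (closing bracket omitted here). It does not mention 4.7.
- Section 4.6.2 adds general latitude: "Dose modifications of oxaliplatin, capecitabine, leucovorin, and fluorouracil are permitted according to local standards or local package inserts".
- The FOLFOX tables in Section 4.6.2.3 have no renal row. The text under them reads "For toxicities not listed above, dose modifications are permitted per local standards".

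**The concern.** A site managing a XELOX subject whose clearance has dropped below 30 mL/min on oxaliplatin can find one section that lowers the dose and another that ends the drug. Nothing in 4.6.2.2 says that its reduction rule stops at some clearance or gives way to 4.7, and nothing in 4.7 refers back.

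This is a safety instruction for a drug given in both arms of the primary comparison. A site that relies on 4.6.2.2 alone could keep a subject on oxaliplatin when 4.7, through 3.5, says it must stop. The handling also feeds reported results: oxaliplatin relative dose intensity (SAP Table 7.4.1-3), chemotherapy dose reductions (SAP 7.4.2.3) and adverse events leading to discontinuation (SAP 7.6.3). The 4.5.2.2 pointer serves only one arm, so the two arms could be handled differently in an open-label trial. The documents do not show that this happened or how often it could.

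**Working it through.** No arithmetic applies. The check sets the two rules side by side by clearance range, cause of the decline and regimen.

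**Inputs**

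1. Reduction rule (4.6.2.2): XELOX only, triggered by severe renal impairment, any cause, action 75% of initial dose.
2. The only clearance boundary beside it (4.6.2.2): normal, mild or moderate means CrCl above 50 mL/min, full dose. By elimination *severe* would begin at 50 or below, but this is not written.
3. Discontinuation rule (4.7): triggered by CrCl below 30 mL/min **and** an oxaliplatin-related decrease; not limited to one regimen.
4. FOLFOX (4.6.2.3): no renal row; unlisted toxicities go to local standards.

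**Two readings of severe.** Reading A takes CrCl at or below 50 mL/min, as the first bullet of 4.6.2.2 implies. Reading B takes CrCl below 30 mL/min, which is an assumption made only to test sensitivity.

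| Case | Reading A | Reading B | Result |
|---|---|---|---|
| XELOX, CrCl above 50 | Full dose | Full dose | No conflict |
| XELOX, CrCl 30 to 50 | 75% rule only | Neither rule | Ambiguous, no conflict |
| XELOX, CrCl below 30, not oxaliplatin-related | 75% rule only | 75% rule only | No conflict |
| XELOX, CrCl below 30, oxaliplatin-related | 75% rule and discontinuation | 75% rule and discontinuation | **Conflict** |
| FOLFOX, CrCl below 30, oxaliplatin-related | Discontinuation only | Discontinuation only | No conflict with 4.6.2.2 |

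The instructions collide in one row, and they do so under both readings. The result there does not depend on how *severe* is defined.

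**Does the Protocol rank the rules?** Section 3.5 makes the 4.7 criteria compulsory for all subjects, which points one way. Section 4.5.2.2 tells nivolumab-plus-chemotherapy sites that chemotherapy discontinuation criteria are in 4.6.2.2 and 4.6.2.3. Section 4.6.2.2 does contain oxaliplatin stopping rules, for neuropathy, so a reader sent there could take it as complete; its renal text speaks only of reduction. The two pointers therefore lead to different instructions for the same subject in that arm.

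**Does local latitude settle it?** Section 4.6.2 covers dose modification. The investigator discretion at the end of 4.7 covers toxicities that the section does not list, and the clearance fall is listed.

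**Can a subject be in the 30 to 50 range from the start?** Yes. The renal entry criterion in Section 3.3.1 is met by serum creatinine up to 1.5 times the upper limit of normal *or* CrCl above 50 mL/min, so a subject can qualify on creatinine with a lower clearance that oxaliplatin did not cause.

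**The case against.** The best defence is that the rules are tiered. Section 4.6.2.2 is adjustable dose guidance, phrased as what should be done. Section 4.7 is phrased as a requirement, and 3.5 makes it compulsory. Stopping criteria laid over dose guidance are an ordinary structure, and stopping need not contradict a lesser step. The triggers also differ: 4.6.2.2 turns on renal status whatever the cause, 4.7 on a drug-related fall to a stated value.

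Much of this stands. The difference in triggers limits the conflict to one subset, and 3.5 makes the tiered reading plausible. But the tiers are never stated: 4.6.2.2 neither stops at 30 mL/min nor defers to 4.7. The 4.5.2.2 pointer bypasses 4.7 for the arm that most needs the ranking to be explicit. The two sections also differ on neuropathy: 4.6.2.2 stops oxaliplatin at Grade 3 or greater peripheral sensory neuropathy, while 4.7 names Grade 4 or greater peripheral neuropathy, or persistent Grade 3 paraesthesia. That is more consistent with sections that were not harmonised than with a planned hierarchy.

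Three stronger readings are tempting, and the documents support none of them.

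- A reader might infer that 4.7 stops oxaliplatin for severe renal impairment in general. It does not; it requires an oxaliplatin-related fall below 30 mL/min.
- A reader might infer that 30 to 50 mL/min is covered by no rule. The first renal bullet in 4.6.2.2 implies that *severe* starts at 50 or below, which would place that range under the reduction rule. The gap appears only if another definition is brought in.
- A reader might infer that every XELOX subject falling below 50 mL/min is affected. Between 30 and 50 there are no opposing instructions, and below 30 the cause matters.

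**Conclusion.** The point holds in a narrow form. For XELOX subjects with an oxaliplatin-related CrCl below 30 mL/min, 4.6.2.2 and 4.7 give incompatible instructions, and the pointers in 3.5 and 4.5.2.2 leave precedence unclear for the nivolumab-plus-chemotherapy arm. The missing clearance limit for *severe* is a separate ambiguity affecting 30 to 50 mL/min.

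The conclusion rests on reading both sentences literally and on *severe* including clearance below 30 mL/min, which is true under both readings tested. The number of subjects affected cannot be estimated from the documents. No endpoint definition, sample size, power or alpha figure changes, and no between-arm bias is demonstrated. It is an internal inconsistency in a safety instruction that should be corrected. Nothing here says which clinical rule is right.

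**What to change.** Reconcile Sections 4.6.2.2 and 4.7 together with the cross-references in 4.5.2.2 and 3.5. The revised text should state:

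1. the CrCl range meant by severe renal impairment in 4.6.2.2;
2. whether the cause of the decline changes the instruction;
3. which section takes precedence when both apply;
4. the same location for chemotherapy discontinuation criteria in 4.5.2.2 and 3.5.

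It would be sensible to confirm at the same time that the absence of a renal row for FOLFOX in 4.6.2.3 is intended. The clinical team sets the ranges and actions. The cost is protocol clarification wording; no analysis or sample size work is needed.
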